5.2.2.2.3. Sensitivity Estimator 3 For the Main Estimand (Missing as Non-response)

For this sensitivity estimator 3, the same statistical model (stratum-adjusted MH test), and data included will be used as for the main estimator (Section 5.2.2.1). The assumption for missing data and the rule to handle missing data have changed.

5.2.2.2.3.1. Assumptions

- Missing Data for HBsAg are Missing Not at Random
- The treatment effect is homogeneous across strata

5.2.2.2.3.2. Missing Data Handling Rule

For sensitivity estimator 3, participants who withdraw from the study prior to Week 72 will be considered as non-responders. After taking into account all the intercurrent events and applying the intercurrent event strategies specified in Section 5.2.2, if a subject who did not experience any ICEs has missing response status for the primary endpoint then the primary endpoint status will be imputed as non-responders.

5.2.2.2.4. Sensitivity Estimator 4 For the Main Estimand (Tipping Point)

For this sensitivity estimator 4, the same statistical model (stratum-adjusted MH test), and data included will be used as for the main estimator (Section 5.2.2.1). The assumption for missing data and the rule to handle missing data have changed.

5.2.2.2.4.1. Assumptions

- Missing Data for HBsAg are Missing Not at Random (MNAR)
- The treatment effect is homogeneous across strata

5.2.2.2.4.2. Missing Data Handling Rule

For sensitivity estimator 4, after taking into account all the intercurrent events and applying the intercurrent event strategies specified in Section 5.2.2, the tipping point approach with the exhaustive scenario's analysis will be applied.

For participants with missing response data at Week 72, responder status will be imputed in an increasing manner by participant count for each treatment group. Specifically, for each participant with missing data at Week 72, a responder/non-responder status will be imputed starting with the scenario where all participants are non-responders up to the scenario where all participants are responders. This would include all possible scenario combinations of responder/non-responder status for all missing data, including scenarios where participants on JNJ-3989+JNJ-6379+NA have worse outcomes than participants on placebo+placebo+NA. Within the exhaustive scenarios list, the 'worst case scenario' will be one of the cases where all participants with missing Week 72 data in the JNJ-3989+JNJ-6379+NA arm will be imputed to 'non-responders' and all participants with missing data at Week 72 in the placebo+placebo+NA arm will be imputed to "responders". For each scenario, the same statistical model (stratum-adjusted MH test), will be used as for the

main estimator of the comparisons vs control (Section 5.2.2.1.1). A graphical display of the p-value significance will summarize the results across all scenarios for the tipping point analysis.

5.2.2.3. Supplementary Estimators of the Main Estimand

Supplementary analyses to better interpret the results will be conducted by constructing additional estimators for the main estimand of the primary endpoint as defined in Section 5.2.2. This estimator will be based on the ITT set (instead of mITT).

To provide a comprehensive interpretation of the study results and the impact of COVID-19 pandemic on the functional cure at Week 72, the following supplementary estimators will utilize the ITT analysis set.

5.2.2.3.1. Supplementary Estimator 1 (ITT Analysis Set + MI)

For this supplementary estimator, the same estimand defined in Section 5.2.2, statistical model (stratum-adjusted MH test), and assumptions will be used as for the main estimator (Section 5.2.2.1).

The missing data approach will follow the MI approach as described in (Section 5.2.2.1.4).

All available data from ITT analysis set, after taking into account all the intercurrent events and applying the intercurrent event strategies specified in Section 5.2.2, will be included.

5.2.2.3.2. Supplementary Estimator 2 (ITT Analysis Set + LOCF)

For this supplementary estimator, the same estimand defined in Section 5.2.2, statistical model (stratum-adjusted MH test), and assumptions will be used as for the main estimator (Section 5.2.2.1).

The missing data approach will follow the LOCF approach as described in Section 5.2.2.2.2.

All available data from ITT analysis set, after taking into account all the intercurrent events and applying the intercurrent event strategies specified in Section 5.2.2, will be included.

5.2.2.3.3. Supplementary Estimator 3 (ITT Analysis Set + Missing as Non-Response)

For this supplementary estimator, the same estimand defined in Section 5.2.2, statistical model (stratum-adjusted MH test), and assumptions will be used as for the main estimator (Section 5.2.2.1).

The missing data approach will follow the missing as non-response approach as described in Section 5.2.2.3.2.

All available data from ITT analysis set, after taking into account all the intercurrent events and applying the intercurrent event strategies specified in Section 5.2.2, will be included.

5.2.2.3.4. Supplementary Estimator 4 (ITT Analysis Set + Tipping Point)

For this supplementary estimator, the same estimand defined in Section 5.2.2, statistical model (stratum-adjusted MH test), and assumptions will be used as for the main estimator (Section 5.2.2.1).

This supplementary estimator will use the tipping point approach as described in Section 5.2.2.2.4.2.

All available data from ITT analysis set, after taking into account all the intercurrent events and applying the intercurrent event strategies specified in Section 5.2.2, will be included.

5.2.3. Supplementary Estimand for the Primary Endpoint (Per-Protocol Analysis Set)

A) Study Intervention:

- Arm 1: JNJ-3989 (200 mg) + JNJ-6379 (250 mg qd) + NA
- Arm 2: Placebo + Placebo + NA

B) Study Population: HBeAg-negative chronic HBV-infected patients who are virologically suppressed by being treated with NA and who are able to tolerate the treatment regimen and will comply with the treatment schedule as prescribed.

C) Variable: Response status defined as participants who meet the criteria defining functional cure at Week 72 (responders) as in Section 5.2.1

D) Intercurrent events:

- Treatment discontinuation prior to Week 48: if the participant discontinued treatment prior to Week 48 then s/he will be considered non-responder (composite strategy).
- Deaths prior to Week 72 are handled in a composite strategy as participants who die prior to Week 72 will be considered as non-responders.
- NA re-treatment between Week 48 and 72: the participant will be counted as non-responder (composite strategy).

E) Population-level summary: Difference in proportion of participants with functional cure status at Week 72 between study intervention arms.

5.2.3.1. Main Estimator

5.2.3.1.1. Analysis Methods

Similar stratum-adjusted MH test on the difference of proportions as described for the main estimator of the main estimand will be used (see section 5.2.2.1.1).

5.2.3.1.2. Data Included

All available data from randomized participants that are included in the PP analysis set will be used, after taking into account the intercurrent events and applying the intercurrent event strategies specified in Section 5.2.3.

To complement this analysis because of its inherent bias and allow a better interpretation of the results, the proportions of participants excluded from the PP analysis set will be summarized by intervention arm and by type of major protocol deviation.

5.2.3.1.3. Assumptions

- The treatment effect is homogeneous across strata

5.2.3.1.4. Missing Data Handling Rule

Participants who withdraw from the study prior to Week 72 will be considered non-responders. For the participants still in the study at Week 72 or for participants that have neither discontinued treatment early nor experienced any major protocol violations as listed in [Attachment 1](#), but HBsAg values missing at Week 72, then the primary method to handle missing data will be the imputation to non-responder.

5.2.4. Subgroup Analyses of the Primary Endpoint

The potential association between the functional cure rate and the randomization stratification factors will be explored by a logistic regression model and exploration of the interaction terms using observed case data. The model will include intervention arm, screening HBsAg level, race and type of NA, as factors, and the intervention arm-by-HBsAg level, intervention arm-by-race, and intervention arm-by-type of NA interaction terms. The functional cure rate estimates for each intervention arm will be derived from this model and presented graphically with their 90% CI in a forest plot.

In addition, for assessment of internal consistency and investigation of homogeneity of the treatment effect in the primary efficacy endpoint across other subgroups (as defined in Section 2.4.1), similarly to what is described above, a logistic regression model ([Brooks ST. et al., 2004](#)) will be estimated for each subgroup variable at a time. The factors in the model will be intervention arm, screening HBsAg level, race, type of NA and the subgroup variable as factors, and the intervention arm-by-subgroup variable as the interaction-term ([Brooks ST. et al., 2004](#)). Corresponding 90% CIs will be also calculated without multiplicity adjustment for each intervention arm. Statistical analysis of treatment heterogeneity between subgroups will be conducted by assessing the significance of the interaction term. The forest plot will present graphically the primary endpoint estimate, its 90% CI resulting from the model across intervention arms by the prespecified subgroups.

Tabulations of the primary endpoint by intervention arm and predefined subgroups will be used to summarize the data descriptively.

5.3. Major Secondary Endpoints

See Section 1.1 for a list of the secondary endpoints. All major secondary endpoints will be analyzed using observed case data. Additional analyses with specific imputation methods for missing data are added for selected endpoints.

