5.3.1. Definitions

5.3.1.1. Binary Endpoints

Analyses described below as being with emphasis are for endpoints at selected time points. These analyses will utilize imputation methods for handling missing data and will be compared between study intervention arms (see Section 5.3.2.1).

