5.3.1.1.1. HBsAg Sero clearance

Sero clearance of HBsAg is defined as HBsAg level <LLOQ. HBsAg sero clearance may be achieved prior to the time point assessed but must be observed at the given week of interest.

HBsAg sero clearance will be evaluated over all time points when assessed, with emphasis at the following time points:

- at Week 48
- at Week 96 (ie, 48 weeks after completion of all study interventions at Week 48) without restarting NA treatment,
- 24 weeks after stopping all study interventions (regardless when intervention was stopped) without restarting NA treatment, and
- 48 weeks after stopping all study interventions (regardless when intervention was stopped) without restarting NA treatment

If the HBsAg value at Week 48 is missing, the LOCF approach will be used with the condition that no value earlier than Week 40 may be carried forward.

For the analyses of sero clearance 24 and 48 weeks after stopping all study intervention respectively, participants with HBsAg sero clearance at the respective time points, and without restarting NA treatment will be considered as having achieved this endpoint. If HBsAg values are missing, then LOCF in conjunction with the next available observation (if available for 48 weeks after stopping all study interventions) imputation approach will be used. The available non-missing HBsAg value closest to the time point which is no earlier/later than 12 weeks prior/after to the respective time point will be used.

For the analyses of sero clearance at Week 96 participants with HBsAg sero clearance at the respective time points, and without restarting NA treatment will be considered as having achieved this endpoint. If HBsAg values are missing, then LOCF approach will be used. The available non-missing HBsAg value closest to the time point which is no earlier than 12 weeks prior to the respective time point will be used.

For all other time points, seroclearance will be analyzed as observed case without imputation.

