5.4. Exploratory Endpoints

5.4.1. Definitions

5.4.1.1. Binary Endpoints

5.4.1.1.1. Partial Cure

Partial cure will be evaluated at each of the following time points separately: 24 weeks and 48 weeks after stopping all study interventions. A participant will be defined as having achieved partial cure if he/she has:

- Stopped all study interventions at any time, and
- had HBV DNA level $< 2,000$ IU/ml quantifiable at the given week of interest, and
- had HBsAg \geq LLOQ at the given week of interest, and
- not required NA re-treatment after stopping all study interventions.

If the HBV DNA or HBsAg value 24 weeks after stopping all study interventions is missing, the LOCF in conjunction with the next available observation imputation approach will be used. The available non-missing lab test closest to 24 weeks after stopping all study interventions which is no earlier/later than 12 weeks from the actual time point of interest (12 and 36 weeks after stopping all study interventions, respectively) will be imputed. If a subject does not have data within 12 and 36 weeks after stopping all study interventions then the subject will be considered as a non-responder.

If the HBV DNA or HBsAg value at 48 weeks after stopping all study interventions is missing, the LOCF imputation approach will be used. The last available lab test no earlier than 36 weeks after stopping all study interventions will be carried forward. If a subject does not have data 36 weeks after stopping all study interventions then the subject will be considered as a non-responder.

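### The secondary seroclearance endpoints have no rule for participants without an HBsAg value in the imputation window, so the SAP's observed-case default would most naturally drop them from the denominator

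*SAP*

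**What the plan says.** SAP 5.3 sets the default: "All major secondary endpoints will be analyzed using observed case data". It then adds that "Additional analyses with specific imputation methods for missing data are added for selected endpoints". SAP 5.3.1.1 says of the emphasised time points: "These analyses will utilize imputation methods for handling missing data and will be compared between study intervention arms".

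SAP 5.3.1.1.1 gives the imputation rules for seroclearance:

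- **Week 48:** "the LOCF approach will be used with the condition that no value earlier than Week 40 may be carried forward".
- **24 and 48 weeks after stopping all interventions, whenever that was:** the closest value within 12 weeks either side, where a later one exists.
- **Week 96:** the closest value from the preceding 12 weeks.
- **Elsewhere:** "For all other time points, seroclearance will be analyzed as observed case without imputation".

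None of the first three says what to do if no value qualifies, and none says how a study withdrawal is counted. SAP 5.3.2.1 lists these four endpoints for a stratified Mantel-Haenszel comparison between arms and names no denominator. Protocol 9.4.1.2 plans the same kind of comparison; the protocol states its non-responder rule only for the primary endpoint (9.4.1.1).

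**The concern.** A windowed imputation rule needs a last step for the participant whose window is empty. Without one, the general rule applies, and here that is observed case. A participant with no qualifying value would then count neither as a success nor as a failure. Because the endpoint is the presence of a response, leaving out people who mostly did not respond raises the rate. It raises it most in the arm that loses more people.

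The gap stands out because the SAP closes it elsewhere, even for an exploratory endpoint. It also leaves the denominator to be settled late: the sponsor's central study team is unblinded at the Week 48 interim analysis (SAP 1.5), before the Week 96 results exist.

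**Working it through.** **1. The plan's own figure.** SAP 1.4 claims more than 91% power for 80 vs 40 participants, 25% vs 5%, one-sided alpha 0.05. Exact binomial enumeration of the unstratified Mantel-Haenszel test gives 91.7%, which agrees. It concerns the primary endpoint and is not touched by this point. No figure is stated for the secondary endpoints.

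**2. Where the SAP finishes the rule and where it does not.**

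| SAP section | Endpoint | If no usable value |
|---|---|---|
| 5.2.2.1.4 | Primary, main estimator | Withdrawal before Week 72: non-responder. Still in study, no intercurrent event: multiple imputation |
| 5.2.2.2.2 | Primary, LOCF sensitivity | Nothing within 12 weeks either side: non-responder |
| 5.4.1.1.1 | Partial cure (exploratory) | Nothing in the window: "then the subject will be considered as a non-responder" |
| 5.4.1.1.4 | Finite-duration analysis | All missing: non-responder |
| 5.3.1.1.1 | Seroclearance, four secondary time points | Not stated |

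The second and third rows use nearly the same windows as 5.3.1.1.1 and then complete them.

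**3. Who is affected.** Participants who withdraw from the study before the window opens have no value in it. Early treatment discontinuers who stay in follow-up are different. Protocol 4.1 keeps them under assessment for 48 weeks after their last treatment. SAP Table 1 ends the double-blind phase at the maximum of last intake and Week 48, which can be read two ways:

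- *Phase runs to Week 48 for everyone.* A sample taken on days 324-350 maps to Week 48, so that endpoint is filled. Someone who stops before about Week 36 finishes follow-up before Week 84 (36 + 48 = 84), and Week 84 is where the Week 96 window opens (96 - 12 = 84). Week 96 is then empty.
- *Phase ends at discontinuation.* The Follow-up Week 48 visit maps to analysis Week 96, so that endpoint is filled. Someone who stops before Week 40 has no double-blind value from Week 40 on, so Week 48 is empty.

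In addition, Protocol 4.1 calls for NA to continue after early discontinuation (7.1 also allows it to be stopped), and 6.6 foresees participants who cannot stop NA at Week 48. For anyone who never stops NA, the two after-stopping endpoints have no starting date.

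**4. Size.** Inputs: N = 80 and 40; planning rates 25% and 5% (SAP 1.4, for Week 72), that is 20 and 2 responders. The fraction dropped, d, is an assumption because neither document states a dropout rate. Every dropped participant is taken to be a non-responder.

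Non-response rule: rate = responders / N. Observed case: rate = responders / [N(1 - d)].

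| d, Arm 1 / control | Arm 1 | Control | Difference (points) |
|---|---|---|---|
| 0 / 0 | 20/80 = 25.0% | 2/40 = 5.0% | 20.0 |
| 5% / 5% | 20/76 = 26.3% | 2/38 = 5.3% | 21.1 |
| 10% / 10% | 20/72 = 27.8% | 2/36 = 5.6% | 22.2 |
| 15% / 15% | 20/68 = 29.4% | 2/34 = 5.9% | 23.5 |
| 20% / 20% | 20/64 = 31.25% | 2/32 = 6.25% | 25.0 |
| 15% / 5% | 20/68 = 29.4% | 2/38 = 5.3% | 24.1 |
| 5% / 15% | 20/76 = 26.3% | 2/34 = 5.9% | 20.4 |

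With no true effect (5% in both arms), equal dropout creates no difference. Dropout of 15% vs 5% gives 4/68 = 5.9% vs 2/38 = 5.3%, a spurious 0.6 points.

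**The case against.** The strongest reply is that the SAP is silent here. It nowhere says that a participant whose window is empty reverts to observed case or leaves the denominator. It reserves observed case without imputation for the other time points. It also requires seroclearance to be seen at the week in question, reports the proportion achieving the endpoint, and names mITT as the analysis set. On that reading, no value means not achieved, and the result is already non-response. This is tenable, and it means the defect is an unspecified rule, not a stated exclusion. It does not remove the point, because 5.3 states observed case for all major secondary endpoints and nothing in 5.3.1.1.1 overrides it for an empty window.

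Three stronger readings are tempting, and the documents do not support them:

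- *Early discontinuers are dropped as a class.* They stay in follow-up unless they withdraw consent, and the two after-stopping endpoints include them whenever they stopped. They are at risk at Week 48 or Week 96, depending on how Table 1 is read, or if they never stop NA.
- *The primary endpoint treats all missing values as non-response.* It uses multiple imputation for participants still in the study without an intercurrent event, and mITT removes COVID-related withdrawals and missing assessments. The contrast holds for withdrawals and for the LOCF sensitivity estimator.
- *The gap makes Week 48, 72 and 96 rates non-comparable.* They already differ by design: Week 48 has no condition on restarting NA, and Week 72 counts stopping treatment before Week 48 as failure.

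It is also fair to say that these are secondary comparisons without multiplicity adjustment. That limits the consequence.

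**Conclusion.** The point holds as a missing last step in the rule for four between-arm secondary comparisons. Followed as written, the observed-case default most naturally applies to participants with an empty window, contrary to how the SAP treats comparable cases elsewhere. Under assumed equal dropout of 5-20%, the planned 20-point difference would read as 21.1 to 25.0 points. With unequal dropout it would be 24.1 (15% vs 5%) or 20.4 (5% vs 15%), so the effect on the difference depends heavily on which arm loses more.

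These sizes are illustrative. They rest on assumed dropout, on Week 72 planning rates applied to other time points, and on every dropped participant being a non-responder, which makes each arm's rate an upper bound for its dropout level. The documents do not allow the real inflation to be estimated. The change is a cheap improvement.

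**What to change.** In SAP 5.3.1.1.1:

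1. State that a participant who withdrew from the study before the time point, or who has no HBsAg value after the stated carry-forward or nearest-value rule, counts as a non-responder. All mITT participants stay in the denominator, and all ITT participants in the supplementary analysis.
2. State how participants who never stop NA are counted in the 24- and 48-weeks-after-stopping endpoints.
3. Keep the observed-case analysis as a sensitivity analysis.

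Clarifying in Table 1 when the double-blind phase ends for an early discontinuer would also settle which visits can fill Week 48 and Week 96.

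The cost is a few sentences of SAP text and no new data. The downside is that the reported rates become slightly less favourable.

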5.3.1. Definitions

5.3.1.1. Binary Endpoints

Analyses described below as being with emphasis are for endpoints at selected time points. These analyses will utilize imputation methods for handling missing data and will be compared between study intervention arms (see Section 5.3.2.1).

5.3.1.1.1. HBsAg Sero clearance

Sero clearance of HBsAg is defined as HBsAg level <LLOQ. HBsAg sero clearance may be achieved prior to the time point assessed but must be observed at the given week of interest.

HBsAg sero clearance will be evaluated over all time points when assessed, with emphasis at the following time points:

- at Week 48
- at Week 96 (ie, 48 weeks after completion of all study interventions at Week 48) without restarting NA treatment,
- 24 weeks after stopping all study interventions (regardless when intervention was stopped) without restarting NA treatment, and
- 48 weeks after stopping all study interventions (regardless when intervention was stopped) without restarting NA treatment

If the HBsAg value at Week 48 is missing, the LOCF approach will be used with the condition that no value earlier than Week 40 may be carried forward.

For the analyses of sero clearance 24 and 48 weeks after stopping all study intervention respectively, participants with HBsAg sero clearance at the respective time points, and without restarting NA treatment will be considered as having achieved this endpoint. If HBsAg values are missing, then LOCF in conjunction with the next available observation (if available for 48 weeks after stopping all study interventions) imputation approach will be used. The available non-missing HBsAg value closest to the time point which is no earlier/later than 12 weeks prior/after to the respective time point will be used.

For the analyses of sero clearance at Week 96 participants with HBsAg sero clearance at the respective time points, and without restarting NA treatment will be considered as having achieved this endpoint. If HBsAg values are missing, then LOCF approach will be used. The available non-missing HBsAg value closest to the time point which is no earlier than 12 weeks prior to the respective time point will be used.

For all other time points, seroclearance will be analyzed as observed case without imputation.

